5.2.3 Trial Blinding/Masking

This is an open-label trial; therefore, the Sponsor, investigator and subject will know the treatment administered.

The study team will be blinded to PD-L1 expression status (positive or negative) for all subjects participating in the initial all-comers portion of Cohort 1 until the interim analysis of Cohort 1. Following the interim analysis, the Sponsor will be unblinded to PD-L1 data. Analyses or summaries of PD-L1 biomarker status will be limited and documented after the interim analysis. See additional details regarding blinding in Section 8.2.

5.3 Randomization or Treatment Allocation

Subjects participating in this trial will be allocated by non-random assignment.

5.4 Stratification

No stratification based on age, sex or other characteristics will be used in this trial.

5.5 Concomitant Medications/Vaccinations (Allowed & Prohibited)

Medications or vaccinations specifically prohibited in the exclusion criteria are not allowed during the ongoing trial. If there is a clinical indication for any medication or vaccination specifically prohibited during the trial, discontinuation from trial therapy or vaccination may be required. The investigator should discuss any questions regarding this with the Sponsor Clinical Director. The final decision on any supportive therapy or vaccination rests with the investigator and/or the subject's primary physician. However, the decision to continue the subject on trial therapy or vaccination schedule requires the mutual agreement of the investigator, the Sponsor and the subject.

5.5.1 Acceptable Concomitant Medications

All treatments that the investigator considers necessary for a subject's welfare may be administered at the discretion of the investigator in keeping with the community standards of medical care. All concomitant medication will be recorded on the electronic case report form (eCRF) including all prescription, over-the-counter (OTC), herbal supplements, and IV medications and fluids. If changes occur during the trial period, documentation of drug dosage, frequency, route, and date may also be included on the eCRF.

All concomitant medications received within 28 days before the first dose of trial treatment and 30 days after the last dose of trial treatment should be recorded. Concomitant medications administered 30 days after the last dose of trial treatment should be recorded for SAEs and ECIs as defined in Section 7.2.

5.5.2 Prohibited Concomitant Medication

Subjects are prohibited from receiving the following therapies during the Screening and for the duration of the study (including Second Course Phase) of this trial:

- Antineoplastic systemic chemotherapy or biological therapy not specified in this protocol
- Immunotherapy not specified in this protocol
- Investigational agents other than pembrolizumab
- Radiation therapy
 - Note: Radiation therapy to a symptomatic solitary lesion or to the brain may be allowed after consultation with Sponsor.
- Live vaccines within 30 days prior to the first dose of trial treatment and while participating in the trial. Examples of live vaccines include, but are not limited to, the following: measles, mumps, rubella, varicella/zoster, yellow fever, intranasal influenza, rabies, BCG, and typhoid vaccine.
- Systemic glucocorticoids for any purpose other than to modulate symptoms from an AE of suspected immunologic etiology. The use of physiologic doses of corticosteroids (prednisone 10 mg or equivalent) may be approved after consultation with the Sponsor.

Note 1: For the purpose of preventing chemotherapy-induced nausea/vomiting, the administration of dexamethasone should be limited to those instances when the subject is receiving high (or moderate) emetic risk chemotherapy (Cohort 2). The dose and duration of dexamethasone administration should be limited to the lowest needed to prevent and/or treat chemotherapy-related nausea and emesis.

Note 2: Anti-emetic prophylaxis with corticosteroids per NCCN or institutional guideline is permitted.

Subjects who, in the assessment by the investigator, require the use of any of the aforementioned treatments for clinical management should be removed from the trial. Subjects may receive other medications that the investigator deems to be medically necessary.

Concomitant Medications to be used with caution:

- Cimetidine, metronidazole and interferons may increase levels of 5-FU.
- Subjects who are taking phenytoin in conjunction with 5-FU should be examined regularly due to a potential elevation in phenytoin plasma levels. Hepatotoxic effects (rise in alkaline phosphatase, transaminase, or bilirubin levels) are commonly observed under the treatment with 5-FU and levamisole.

The Exclusion Criteria describes other medications which are prohibited in this trial.

There are no prohibited therapies during the Post-Treatment Follow-up Phase.

5.6 Rescue Medications & Supportive Care

5.6.1 Supportive Care Guidelines for Pembrolizumab

Subjects should receive appropriate supportive care measures as deemed necessary by the treating investigator. Suggested supportive care measures for the management of AEs with potential immunologic etiology are detailed in Section 5.2.1.2.3, [Table 4](#). Where appropriate, these guidelines include the use of oral or intravenous treatment with corticosteroids as well as additional anti-inflammatory agents if symptoms do not improve with administration of corticosteroids. Note that several courses of steroid tapering may be necessary as symptoms may worsen when the steroid dose is decreased. For each disorder, attempts should be made to rule out other causes such as metastatic disease or bacterial or viral infection, which might require additional supportive care. The treatment guidelines are intended to be applied when the investigator determines the events to be related to pembrolizumab.

It may be necessary to perform conditional procedures such as bronchoscopy, endoscopy, or skin photography as part of evaluation of the event.

5.6.2 Supportive Care Guidelines for Chemotherapy Agents

Pre-cisplatin treatment with corticosteroids per NCCN or institutional guidelines is permitted for subjects in Cohort 2.

Please refer to the product label or local standards of care for additional supportive measures for cisplatin, 5-FU, and capecitabine (Japan only).

5.7 Diet/Activity/Other Considerations

5.7.1 Diet

Subjects should maintain a normal diet unless modifications are required to manage an AE such as diarrhea, nausea or vomiting.

5.7.2 Contraception

Pembrolizumab may have adverse effects on a fetus in utero. Furthermore, it is not known if pembrolizumab has transient adverse effects on the composition of sperm. Non-pregnant, non-breast-feeding women may be enrolled if they are willing to use 2 methods of birth control or are considered highly unlikely to conceive. Highly unlikely to conceive is defined as 1) surgically sterilized, or 2) postmenopausal (a woman who is ≥ 45 years of age and has not had menses for greater than 1 year will be considered postmenopausal), or 3) not heterosexually active for the duration of the study. The two birth control methods can either be two barrier methods or a barrier method plus a hormonal method to prevent pregnancy.

Subjects in Cohorts 1 & 3 should start using birth control from study Visit 1 throughout the study period up to 120 days after the last dose of study treatment. Subjects in Cohort 2 should start using birth control from study Visit 1 throughout the study period up to 180 days after the last dose of study treatment.

The following are considered adequate barrier methods of contraception: diaphragm, condom (by the partner), copper intrauterine device, sponge, or spermicide as per local regulations or guidelines. Appropriate hormonal contraceptives will include any registered and marketed contraceptive agent that contains an estrogen and/or a progestational agent (including oral, subcutaneous, intrauterine, or intramuscular agents).

Abstinence is acceptable if this is the usual lifestyle and preferred contraception for the subject.

Subjects should be informed that taking the study medication may involve unknown risks to the fetus (unborn baby) if pregnancy were to occur during the study. In order to participate in the study they must adhere to the contraception requirement (described above) for the duration of the study and during the follow-up period defined in Section 7.2.2 - Reporting of Pregnancy and Lactation to the Sponsor. If there is any question that a subject will not reliably comply with the requirements for contraception, that subject should not be entered into the study.

5.7.3 Use in Pregnancy

If a subject inadvertently becomes pregnant while on treatment with study treatment, the subject will immediately be removed from the study. The site will contact the subject at least monthly and document the subject's status until the pregnancy has been completed or terminated. The outcome of the pregnancy will be reported to the Sponsor without delay and within 24 hours if the outcome is a serious adverse experience (e.g., death, abortion,

congenital anomaly, or other disabling or life-threatening complication to the mother or newborn). The study investigator will make every effort to obtain permission to follow the outcome of the pregnancy and report the condition of the fetus or newborn to the Sponsor. If a male subject impregnates his female partner, the study personnel at the site must be informed immediately and the pregnancy reported to the Sponsor and followed as described above and in Section 7.2.2.

5.7.4 Use in Nursing Women

Since many drugs are excreted in human milk, and because of the potential for serious adverse reactions in the nursing infant, subjects who are breast-feeding are not eligible for enrollment. Specific additional information follows for individual agents used in this trial.

5.7.4.1 Pembrolizumab

It is unknown whether pembrolizumab is excreted in human milk.

5.7.4.2 Cisplatin

Cisplatin has been reported to be found in human milk; subjects receiving Cisplatin injection should not breast-feed.

5.7.4.3 5-Fluorouracil

It is not known whether 5-fluorouracil is excreted in human milk. Because 5-fluorouracil inhibits DNA, RNA and protein synthesis, mothers should not nurse while receiving this treatment.

5.7.4.4 Capecitabine (Japan)

Lactating mice given a single oral dose of capecitabine excreted significant amounts of capecitabine metabolites into the milk. It is not known whether capecitabine is excreted in human milk. Subjects receiving capecitabine should not breast-feed.

5.7.5 Photosensitivity

Investigators are advised to counsel subjects assigned to receive capecitabine or 5-FU about the risk of photosensitivity and to take sun protection measures accordingly.

5.8 Subject Withdrawal/Discontinuation Criteria

Subjects may withdraw consent at any time for any reason or be dropped from the trial at the discretion of the investigator should any untoward effect occur. In addition, a subject may be withdrawn by the investigator or the Sponsor if enrollment into the trial is inappropriate, the trial plan is violated, or for administrative and/or other safety reasons. Specific details regarding discontinuation or withdrawal procedures; including specific details regarding withdrawal from Future Biomedical Research, are provided in Section 7.1.4 – Other Procedures.

In this trial, a subject may discontinue from treatment but continue to participate in the regularly scheduled activities, as long as the subject does not withdraw consent. For a subject who has discontinued treatment but is continuing to be monitored in the trial, he/she may be allowed to begin treatment again under certain protocol-defined circumstances if deemed medically appropriate.

A subject must be discontinued from the trial for any of the following reasons:

- The subject or legal representative (such as a parent or legal guardian) withdraws consent.

A subject must be discontinued from treatment (but may continue to be monitored in the trial) for any of the following reasons:

- The subject or legal representative (such as a parent or legal guardian) withdraws consent for treatment
- Confirmed radiographic disease progression per the terms outlined in Section 7.1.2.7.4.1
- Unacceptable adverse experiences as described in Section 5.2.1.2
- Intercurrent illness that prevents further administration of treatment
- Recurrent Grade 2 pneumonitis
- Investigator's decision to withdraw the subject
- The subject has a confirmed positive serum pregnancy test
- The subject is lost to follow-up
- Completed 35 administrations of pembrolizumab (approximately 2 years) of study treatment, whichever is later.

Note: 35 administrations of study medication is calculated from the date of first dose. Subjects who stop study treatment after 35 administrations of pembrolizumab may be eligible for up to one year of additional pembrolizumab if they progress after stopping study treatment provided they meet the requirements detailed in Section 7.1.5.5.

- Administrative reasons

The End of Treatment and Follow-up visit procedures are listed in Section 6 (Trial Flow Chart) and Section 7.1.5 (Visit Requirements). After the end of treatment, each subject will be followed for 30 days for AE monitoring (SAE and ECI will be collected for 90 days after the end of treatment or 30 days after the end of treatment if the subject initiates new anticancer therapy, whichever is earlier, as described in Section 7.2.3.1). Subjects who discontinue for reasons other than progressive disease will have post-treatment follow-up for disease status until disease progression, initiating a non-study cancer treatment, withdrawing consent or becoming lost to follow-up. After documented disease progression each subject will be followed by telephone for overall survival until death, withdrawal of consent, or the end of the study, whichever occurs first.

5.8.1 Discontinuation of Study Treatment after CR

Discontinuation of treatment may be considered for subjects who have attained a confirmed CR that have been treated for at least 8 administrations with pembrolizumab and had at least 2 treatments with pembrolizumab) beyond the date when the initial CR was declared. Subjects who then experience radiographic disease progression may be eligible for up to one year of additional treatment with pembrolizumab via the Second Course Phase at the discretion of the investigator if no cancer treatment was administered since the last dose of pembrolizumab, the subject meets the safety parameters listed in the Inclusion/Exclusion criteria, and the trial is open. Subjects will resume pembrolizumab at the same dose and schedule at the time of initial discontinuation. Additional details are provided in Section 7.1.5.5.

5.9 Subject Replacement Strategy

A subject who discontinues from the trial will not be replaced.

5.10 Beginning and End of the Trial

The overall trial begins when the first subject signs the informed consent form. The overall trial ends when the last subject completes the last study-related phone-call or trial visit, discontinues from the trial or is lost to follow-up (i.e. the subject is unable to be contacted by the investigator). Upon study completion, subjects will be discontinued and may be enrolled in a pembrolizumab extension study. Enrollment in the extension study is conditional on subject consent.

5.11 Clinical Criteria for Early Trial Termination

Early trial termination will be the result of the criteria specified below:

1. Quality or quantity of data recording is inaccurate or incomplete
2. Poor adherence to protocol and regulatory requirements
3. Incidence or severity of adverse drug reaction in this or other studies indicates a potential health hazard to subjects
4. Plans to modify or discontinue the development of the study treatment

In the event of Sponsor decision to no longer supply study treatment, ample notification will be provided so that appropriate adjustments to subject treatment can be made.

6.0 TRIAL FLOW CHART

6.1 Initial Treatment Phase

Trial Period:	Screening	Treatment Cycles ^a (3 weeks per cycle)						End of Treatment (last dose) or Discontinuation	Post-Treatment		
		To be repeated beyond 6 cycles							Safety Follow-up (30 days from last dose)	Follow Up Visits ^b	Survival Follow-up ^f (Phone)
Treatment Cycle/Title:	Visit 1	1	2	3	4	5	6				
Scheduling Window (Days):	-28 to -1		± 3	± 3	± 3	± 3	± 3		± 7	± 7	± 7
Informed Consent	X										
Informed Consent for FBR ^c	X										
Inclusion/Exclusion Criteria	X										
Subject Identification Card	X										
Demographics and Medical History	X										
Prior and Concomitant Medication Review	X	X	X	X	X	X	X	X	X		
Clinical Procedures/Assessments											
Review Adverse Events	X	X	X	X	X	X	X	X	X	X	
12-Lead ECG (Local)	X										
Full Physical Examination	X							X			
Directed Physical Examination		X	X	X	X	X	X				
Ht (V1 only), Wt, & Vital Signs (T/P/RR/BP)	X	X	X	X	X	X	X	X			
ECOG Performance Status	X ^q		X	X	X	X	X	X			
Trial Treatment Administration ^p		X	X	X	X	X	X				
Post-study Anticancer Therapy Status										X	Q12W
Survival Status ^r		←----->									Q12W
LOCAL Laboratory Assessments											
Pregnancy Test – Urine or Serum β-HCG ^d	X										
PT/INR and aPTT ^e	X										
Chemistry Panel ^{e, f}	X		X	X	X	X	X ^f	X	X		
CBC with Differential ^{e, g}	X		X	X	X	X	X ^g	X	X		
T3, FT4, and TSH ^{e, h}	X		X		X		X, then Q2 cycles		X		
Serum carcinoembryonic antigen (CEA) ^{e, i}	X			X		X	X	X			
Urinalysis ^e	X										
CENTRAL Laboratory Assessments											
Blood for Future Biomedical Research ^c		X									
Blood for Proteomics and Genetics ^k		X									
Blood for RNA and DNA Analysis ^k		X	X	X				X			

Trial Period:	Screening	Treatment Cycles ^a (3 weeks per cycle)						End of Treatment (last dose) or Discontinuation	Post-Treatment		
		To be repeated beyond 6 cycles							Safety Follow-up (30 days from last dose)	Follow Up Visits ^b	Survival Follow-up ^f (Phone)
Treatment Cycle/Title:	Visit 1	1	2	3	4	5	6				
Scheduling Window (Days):	-28 to -1		± 3	± 3	± 3	± 3	± 3		± 7	± 7	± 7
Efficacy Measurements											
Tumor Imaging	X ^l				X ^m		X ^m	X ⁿ		X ⁿ	
Tumor Tissue Collection ^o	X	optional biopsy (close to dosing after 9 weeks of treatment)						X ^{optional}			

a. Unless otherwise specified, assessments/procedures are to be performed prior to dose administration on Day 1 of each cycle.

b. Subjects who discontinue study treatment without documented disease progression should continue to be monitored for disease status by radiologic imaging every 6 weeks (± 7 days), and after the 1st year, every 9 weeks (±7 days) until (1) the start of new anti-cancer treatment, (2) disease progression as assessed by the central imaging vendor, (3) death, or (4) the end of the study, whichever occurs first.

c. Informed consent for the optional Future Biomedical Research (FBR) samples must be obtained before the DNA sample is collected. DNA sample for analysis should be obtained predose, on Day 1 (or with the next scheduled blood draw) as the last sample drawn or at a later date as soon as the informed consent is obtained. Detailed instructions for the collection and management of specimens for FBR are provided in the Procedures Manual and Section 12.2.

d. For women of reproductive potential, a negative pregnancy test should be performed within 72 hours prior to first dose of trial treatment. Pregnancy tests (serum and/or urine tests) should be repeated if required by local guidelines.

e. Laboratory Screening Tests should be performed within 3 days prior to first dose of treatment. For all subjects, unresolved abnormal labs resulting in drug-related AEs should be followed until resolution. Post dose lab may be collected up to 72 hours prior to the scheduled time point.

f. Chemistry will be collected on Day 1 of Cycles 2-6, then every 2 cycles. For subjects in Cohort 2 who are receiving chemotherapy, chemistry will be collected every cycle on Day 1. Japan only - for subjects receiving capecitabine, chemistry should be collected as follows for Cycles 1 and 2: Cycle 1 - Days 8 and 15 (screening chemistry labs satisfy requirement for Day 1); Cycle 2 - Days 1, 8, and 15

g. CBC w/differentials will be collected on Day 1 of Cycles 2-6, then every 2 cycles. For subjects in Cohort 2 who are receiving chemotherapy, CBC w/differentials will be collected every cycle on Day 1, 8, and 15 of Cycles 1-6 (screening CBC w/differentials labs satisfy requirement for Day 1 of Cycle 1); then on Day 1 of every cycle thereafter.

h. T3, FT4 and TSH may be analyzed by the central laboratory if cannot be done locally. FT3 may be tested locally (not via central laboratory) if T3 is not locally available

i. On treatment CEA – starting at Cycle 3, CEA will be collected every 2 cycles through Cycle 12, then every 3 cycles until end of treatment.

k. Collect prior to study treatment administration. Whole blood for Genetics/RNA and DNA analyses. Serum and plasma for Proteomics.

l. Tumor imaging at screening: Cohorts 2 & 3 - imaging will be performed within 28 days prior to the first dose of trial treatment. Cohort 1 - imaging will be performed within 14 days prior to the first dose of trial treatment; at sites where the local regulatory body and/or IRB/ERC will not permit a second tumor imaging within a 28-day period, an already available imaging scan obtained within 28 days prior to first dose may be used with the approval of the Sponsor Clinical Director. For all subjects, already available imaging scans performed as part of routine clinical management are acceptable if they are of diagnostic quality and performed within the acceptable timeframe for each cohort.

m. The first on-study tumor imaging will be performed after 9 weeks (±7 days) of study treatment, and then every 6 weeks (±7 days) thereafter (or more frequently if clinically indicated). After 1 year, imaging will be performed every 9 weeks (±7 days). Timing of imaging follows calendar days and should not be adjusted due to dose interruptions. The same imaging technique, acquisition, and processing parameters for a subject should be used throughout the trial. All scans (scheduled and unscheduled) should be submitted to the central imaging vendor as soon as possible after imaging is complete.

n. Subjects without confirmed PD who discontinue treatment will have imaging performed at the time study treatment is discontinued (i.e., date of discontinuation ± 4 week window). If a scan was obtained within 4 weeks prior to discontinuation of treatment, then imaging at treatment discontinuation is not required. Continue to monitor disease status as indicated in Section 7.1.2.7.2. Subjects who discontinue treatment after confirmed PD will not need further imaging performed during the follow-up period.

o. Tumor Tissue collection at screening may be collected up to 42 days prior to first dose of study treatment. An optional newly obtained endoscopic biopsy (if applicable) is requested during the study (preference is as close as possible to dosing after 9 weeks of treatment). An optional biopsy is also requested at the time of discontinuation for PD.

p. Refer to Section 5.2.2 regarding window for timing of dose administrations (for Day 1 Cycle 1 and Cycle 2 onwards).

q. Screening ECOG should be performed within 3 days prior to first dose of study therapy.

Trial Period:	Screening	Treatment Cycles ^a (3 weeks per cycle)						End of Treatment (last dose) or Discontinuation	Post-Treatment		
Treatment Cycle/Title:	Visit 1	1	2	3	4	To be repeated beyond 6 cycles			Safety Follow-up (30 days from last dose)	Follow Up Visits ^b	Survival Follow-up ^f (Phone)
						5	6				
Scheduling Window (Days):	-28 to -1		± 3	± 3	± 3	± 3	± 3	± 3	± 7	± 7	± 7
r. After the start of new anti-cancer treatment or documented disease progression by the central imaging vendor, whichever occurs first, the subject enters the Survival Follow-Up Phase and should be contacted by telephone approximately every 12 weeks to assess for survival status. Updated survival status may be requested by the Sponsor at any time during the course of the study. Upon Sponsor notification, all participants who do not/will not have a scheduled study visit or study contact during the Sponsor-defined time period will be contacted for their survival status (excluding participants that have a death event previously recorded).											

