7.1.2.7 Tumor Imaging and Assessment of Disease

The process for image collection and transmission to the central vendor can be found in the Site Imaging Manual. Tumor imaging may be performed by computed tomography (CT) (preferred) or magnetic resonance imaging (MRI), but **the same imaging technique, acquisition, and processing parameters should be used in a subject throughout the trial.**

All scans, scheduled and unscheduled should be submitted to the central imaging vendor as soon as possible. In determining whether or not the tumor burden has increased or decreased, investigators should consider all target lesions as well as non-target lesions.

A central imaging read based on RECIST 1.1 will be used to determine subject eligibility. The central imaging vendor will receive all images from the sites and conduct the disease assessment. The Sponsor will also receive radiologic images for a retrospective analysis of subject eligibility and treatment response to be performed by the central vendor, using RECIST 1.1. Treatment decisions will be based on the investigator's radiographic assessment of disease, and not based on central imaging vendor's assessment.

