7.1.2.7.2 Tumor Imaging During Trial

The first on-study imaging assessment will be performed at 9 weeks (63 days \pm 7 days) after the first dose of study treatment. Subsequent imaging will be performed every 6 weeks (42 days \pm 7 days), or more frequently if clinically indicated through the first year. After the first year, tumor imaging will be performed every 9 weeks. Tumor imaging will be performed every 6 weeks during the second course treatment.

Imaging should continue to be performed until whichever one of the following occurs first:

- disease progression (refer to [Table 8](#))
- start of new anti-cancer treatment
- withdrawal of consent
- death
- end of study

Imaging should follow calendar days and not be delayed for any dose interruptions that may occur.

Timing of Repeat Imaging

Per RECIST 1.1, response should be confirmed by a repeat radiographic assessment not less than 4 weeks from the date the response was first documented. The scan for confirmation of response may be performed at the earliest 4 weeks after the first indication of response, or at the next scheduled scan (6 weeks later if during the first year or during second course treatment, or 9 weeks later if after the first year during the initial treatment phase), whichever is clinically indicated.

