- If repeat imaging confirms disease progression due to any of the scenarios listed below, subjects will be discontinued from study therapy.
- Tumor burden remains $\geq 20\%$ and at least 5 mm absolute increase compared to nadir
 - Non-target disease resulting in initial disease progression is worse (qualitative)
 - New lesion resulting in initial disease progression is worse (qualitative)
 - Additional new lesion(s) since last evaluation

In determining whether or not the tumor burden has increased or decreased, investigators should consider all target lesions as well as non-target lesions.

When feasible, study treatment should not be discontinued until progression is confirmed. Subjects that are deemed clinically unstable are not required to have repeat imaging for confirmation of progressive disease. Guidance for treatment continuation/discontinuation and repeat imaging per irRECIST is described in [Table 8](#).

Table 8 Imaging and Treatment after 1st Radiologic Evidence of PD

	Clinically Stable		Clinically Unstable	
	Imaging	Treatment	Imaging	Treatment
1 st radiologic evidence of PD	Repeat imaging at ≥ 4 weeks at site to confirm PD	May continue study treatment at the investigator's discretion while awaiting confirmatory scan by site	Repeat imaging at ≥ 4 weeks to confirm PD per physician discretion only	Discontinue treatment
Repeat scan confirms PD	No additional imaging required	Discontinue treatment (exception is possible upon consultation with Sponsor).	No additional imaging required	N/A
Repeat scan shows SD, PR or CR	Continue regularly scheduled imaging assessments	Continue study treatment at the investigator's discretion	Continue regularly scheduled imaging assessments	May restart study treatment if condition has improved and/or clinically stable per investigator's discretion.

CR = complete response; PD = progressive disease; PR = partial response; SD = stable disease

NOTE: If a subject has confirmed radiographic progression (ie, 2 scans at least 4 weeks apart demonstrating progressive disease) per irRECIST, but the subject is achieving a clinically meaningful benefit, an exception to continue treatment may be considered following consultation with the Sponsor.

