7.1.5.4.3 Survival Follow-up

Once a subject experiences confirmed disease progression or starts a new anti-cancer therapy, the subject moves into the Survival Follow-Up Phase and should be contacted by telephone approximately every 12 weeks to assess for survival status until death, explicit withdrawal of consent for survival follow up, or the end of the study, whichever occurs first. Information regarding post-study anti-cancer treatment will be collected if new treatment is initiated.

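### Conflicting triggers end post-treatment scans and start survival follow-up, and the site-PD rule can informatively censor central DOR with no sensitivity analysis planned

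*Combined protocol and SAP*

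**What the plan says.** Two sets of rules govern when scans end and survival follow-up begins.

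**Central reader.** Footnote b of Section 6.1 concerns a limited group: "Subjects who discontinue study treatment without documented disease progression should continue to be monitored for disease status by radiologic imaging". Among its stopping points is "disease progression as assessed by the central imaging vendor". Footnote r moves a subject into survival follow-up "After the start of new anti-cancer treatment or documented disease progression by the central imaging vendor, whichever occurs first". Footnote i of the second-course chart (Section 6.2) repeats footnote r.

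**Site, or no reader named.** Section 7.1.2.7.2 ends imaging at progression as set out in Table 8. There the site confirms progression on a repeat scan, after which the imaging entry reads "No additional imaging required". Footnote n of Section 6.1 says "Subjects who discontinue treatment after confirmed PD will not need further imaging performed during the follow-up period" and sends sites to Section 7.1.2.7.2 for continued monitoring. Section 7.1.5.4.3 starts survival follow-up "Once a subject experiences confirmed disease progression or starts a new anti-cancer therapy".

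On the role of the two readers, Section 7.1.2.7 states: "Treatment decisions will be based on the investigator's radiographic assessment of disease". Section 7.1.2.7.4.1 provides no central confirmation for irRECIST.

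In the analysis, DOR and PFS are read by the central vendor (Section 8.6.1, Table 12). Table 11 gives the DOR censoring rules. The sSAP (Section 3.6.1, Table 2) adds investigator-read RECIST 1.1 versions of ORR, DCR, PFS and DOR.

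**The concern.** Sites need a single answer to whose progression ends imaging, and the protocol gives two. Subjects in the same situation could be scanned for different lengths of time depending on which passage a site follows.

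The second issue concerns the estimate. DOR by central read is a secondary objective in Cohorts 1 and 3 (Section 3.2), but the scans that feed it can be ended by the investigator's call. A responder whom the investigator judges to have progressed is likely to be near a central progression. If scanning stops there and the subject is censored, Kaplan-Meier treats that subject as having the same outlook as responders still followed. The central DOR curve is then too high.

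**Working it through.** **Step 1: apply the rules to three subjects.**

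| Subject | Central-reader passages | Site or unnamed-reader passages | Result |
|---|---|---|---|
| A. Stopped treatment without progression (for example after CR); site confirms progression later, vendor does not | Footnote b: scans go on | 7.1.2.7.2 with Table 8: no more scans required | Direct conflict |
| B. Stopped treatment for site-confirmed progression, vendor does not agree | Footnote b applies only if *documented* means documented centrally; it does not say | Footnote n: no more scans | Conflict depends on an undefined word |
| C. As A or B, no new therapy: when does survival follow-up start? | Footnote r: not yet | 7.1.5.4.3: now | Direct conflict |

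**Step 2: follow A or B, under the site rule, through Table 11 for central DOR.**

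- Alive, no new therapy: censored at the last adequate assessment.
- Alive, new therapy started: censored at the last adequate assessment before it.
- Death after at most one missed assessment: an event.
- Death after two or more missed assessments: censored before the gap. Two scans span 2 × 6 = 12 weeks in year one and 2 × 9 = 18 weeks afterwards. Table 11 does not say whether scans no longer required count as missed. If they do not, the death is a late-dated event, which also lengthens DOR.

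**Step 3: size, for illustration.** The plan states no figure for reader discordance or its effect, so there is nothing to reproduce. Inputs:

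- Median DOR of 24 weeks (6 months), from the KN012 gastric cohort in Section 4.1.3.
- Exponential DOR (assumption).
- Share q of central progressions replaced by censoring (assumption).
- Lead time of the investigator's call over the central progression that continued scanning would have shown (assumption).

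With zero lead, the observed event hazard falls from λ to (1 − q)λ, so the apparent median is 24/(1 − q):

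- q = 10%: 24/0.9 = 26.7 weeks
- q = 20%: 24/0.8 = 30.0 weeks
- q = 30%: 24/0.7 = 34.3 weeks

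Simulated Kaplan-Meier medians (200,000 subjects per scenario) with a lead:

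| q | Lead 0 (formula) | Lead 6 weeks | Lead 12 weeks |
|---|---|---|---|
| 10% | 26.7 | 26.3 | 25.9 |
| 20% | 30.0 | 29.0 | 28.3 |
| 30% | 34.3 | 32.7 | 31.4 |

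The zero-lead formula is the upper end. The bias is upward throughout and shrinks as the lead grows.

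**Step 4: PFS.** Section 8.4.1 counts death as a PFS event, and Table 12 gives only censoring at the last assessment date, with no missed-scan rule. A subject with investigator-only progression who later dies is therefore an event, dated late. Assume a median of 9 weeks to central progression, a further 17 weeks to death, and all deaths observed. The apparent PFS median is then 10.2 weeks at q = 10% and 13.4 weeks at q = 30%. Censoring proper affects only those alive at the data cut-off.

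**The case against.** The strongest reply is that the inconsistency does not cause the bias. Scans are lost because the site rule ends them. Where footnote b applies, it keeps them going. Harmonising every passage on site progression would leave the censoring untouched. This stands, and is why the two issues are kept apart here and the fix has two parts.

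Further points that stand:

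- A reader might infer a clean split between flow chart and text. Footnote n is in the flow chart and follows the confirmed-progression rule, and footnote b covers only subjects who stop without documented progression.
- A reader might infer that sites cannot act on central progression. Section 7.1.2.7 says the vendor receives all images and assesses disease, and separately describes a retrospective vendor analysis. Feedback to sites is not described, and the Site Imaging Manual is not among the documents. Absence of feedback is not established.
- Clinically stable subjects need a repeat scan at least 4 weeks later, which also goes to the vendor. This gives the central reader a second chance to call progression. The safeguard is partial, because Table 8 leaves repeat imaging of clinically unstable subjects to the physician's discretion.
- New anti-cancer therapy ends imaging under both rules, so some of this censoring would remain even with a central trigger.

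The reply that the sSAP's investigator-read DOR already covers the matter stands only in part. That analysis changes the reader for every subject. It does not test how far the central estimate depends on censoring after investigator-only progression.

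**Conclusion.** The triggers conflict and need to be reconciled. The direct conflict is limited to progression arising in post-treatment follow-up and to entry to survival follow-up. Under the site rule, a responder with investigator but no central progression can be censored informatively for central DOR, and the bias is upward.

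The size cannot be established, because the documents give no discordance rate. The range of about 26 to 34 weeks against a 24-week median rests on exponential durations, an assumed 10% to 30% of progressions lost, an assumed lead of 0 to 12 weeks, and a median from another trial with a different regimen. It should not be read as an estimate for this trial.

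Two stronger readings are not supported. One is that PFS is informatively censored in the same way. Table 11 governs DOR only, and later deaths are PFS events, so any PFS bias comes mainly from late-dated events. The other is that a key endpoint is compromised. DOR is secondary, Table 12 calls every Cohort 1 efficacy analysis other than central RECIST 1.1 ORR supportive, and the primary ORR is not shown to be affected. This is a worthwhile, low-cost improvement to a secondary estimate.

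**What to change.** 1. Reconcile footnotes b, n and r of Section 6.1, footnotes f and i of Section 6.2, Section 7.1.2.7.2, Table 8 and Section 7.1.5.4.3. They should name one reader whose progression ends imaging and starts survival follow-up, and footnote b should say who documents progression. Which reader to name is for the sponsor to decide.
2. Whichever is chosen, add to the sSAP a sensitivity analysis of central DOR, and of PFS as supportive. It should count investigator progression as an event on its date when imaging ended without central progression. State in the Table 11 rules whether scans no longer required count as missed.

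The cost is a wording change and one extra analysis. The sSAP already plans investigator-read DOR and PFS, so no new reads are needed. The downside is that a possibly shorter DOR would be reported beside the main estimate.
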